7.2.6.9.3 Handling of missing data

Missing data will not be imputed but will be handled by the underlying MMRM model assuming that the data are MAR.

7.2.6.9.4 Variables

The LSM estimates of the change from baseline to Month 6 of all treatment groups and placebo are taken from the model of the primary efficacy endpoint. In addition, the variance/covariance matrix of the LSM estimates at Month 6 is output by SAS[®]. Both the LSM estimates, and the variance/covariance matrix are transferred into and analyzed using the R *DoseFinding* package.

7.2.6.9.5 Analysis

The analysis will be based on the R-code '*Mods*' and '*MMfit*'.

In the '*Mods* function call' the candidate models are specified, together with the assumed placebo and maximum effects. In the call to the *MCPMod* function,

- *doses* is a vector of length 5, corresponding to Planned Dose for TP1 (increasing order),
- *est* is a vector of length 5, corresponding to the LSM estimates of the change from baseline to Month 6 of all treatment groups and placebo (sorted by dose),
- *C* is the variance/covariance matrix (of dimensions 5×5) of the LSM estimates at Month 6 (sorted by dose),
- *Delta* is a target difference vs. placebo [see protocol section 10.5, [D-22.031](#)].

The object *MMfit* is summarized to obtain the MCP test, parameter estimates, target dose and AIC. These elements will be summarized. The object will be plotted to display the fitted dose-response curves.

The selected model will be fitted using the *fitMod* function and plotted together with the LSM estimates and confidence intervals from the primary analysis.

```
doses <- c(0,0.5,1,2,4)

# define candidate models
mods2 <- Mods(linear = NULL, linlog = NULL, emax = 1, sigEmax = c(1.5, 0.3), logistic =
c(1.5, 0.3), doses = doses, direction="decreasing")

# MCPMod
MMfit <- DoseFinding::MCPMod(type="general", dose=doses, resp=est, S=as.matrix(C),
models=mods2, alpha=0.05, selModel="AIC", Delta=1.5)

# fit the selected model
MMsel <- fitMod(type="general", dose=doses, resp=est, S=as.matrix(C), model=MMfit$selMod)

# extract predicted values to plot, together with CI
pred <- predict(MMsel, se.fit=TRUE, doseSeq=seq(0,4,0.05),predType="ls-means")
pred$LB <- pred$fit - qnorm(0.975)*pred$se.fit
pred$UB <- pred$fit + qnorm(0.975)*pred$se.fit
```

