2 STUDY DESIGN AND FLOW

2.1 Study design

This is a Phase 2b, multicenter, randomized, double-blind, placebo-controlled, parallel group study to evaluate the efficacy, safety, and tolerability of cenerimod in subjects with moderate to severe SLE.

Approximately 325 adult subjects with SLE will be randomized in a 1:1:1:1:1 ratio to placebo, 0.5, 1, 2, or 4 mg once daily of cenerimod, in addition to background SLE therapy.

Once randomized, all subjects will enter a 6-month double-blind study treatment period defined as Treatment Period 1 (TP1).

Subjects randomized to, and still receiving, placebo, 0.5, 1, or 2 mg at Month 6 will continue their study treatment up to an additional maximum of 6 months in Treatment Period 2 (TP2), for a total maximum of 12 months.

Subjects randomized to the 4 mg arm will receive study treatment at this dose for a maximum of 6 months in TP1. Afterwards, subjects in this group, still receiving this dose

at Month 6, will be re-randomized in a 1:1 ratio to placebo or cenerimod 2 mg to enter TP2 and will continue for a total maximum of 12 months

Subjects who discontinue treatment in TP1 will continue study FU, performing study assessments, up to maximum duration of 12 months.

At EOT, subjects will enter a 6-month FU period (4-month before protocol Version 5).

Treatment allocation is stratified by dose of OCS at Randomization (two strata: < 7.5 mg/day or ≥ 7.5 mg/day prednisone or equivalent), and by disease activity at Screening (with two strata: mSLEDAI-2K < 10 or ≥ 10).

The study will be conducted at approximately 180 sites in 21 countries notably from the regions of Asia Pacific, Eastern Europe, Latin America, North America, and Western Europe.

No interim analysis is planned. There will be three study analyses: the Month-6 analysis, the Month-12 analysis and the final EOS analysis. Month-6 analysis will be performed when all randomized subjects have completed TP1 or discontinued the study. Month-12 analysis will be performed when all randomized subjects have completed TP2 or discontinued the study. Final EOS analysis will be performed when all randomized subjects have completed the post-treatment follow-up period or discontinued the study.

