7.2.3 Handling of missing data

Based on the Phase 2 study, AC-064A201, it is expected that 6% of subjects will have a missing mSLEDAI-2K result at Month 6.

Missing data will not be imputed but will be handled by the MMRM assuming that the data are MAR.

Various sensitivity analyses will be performed to evaluate the robustness of this assumption [see [Table 5](#)].

A summary of the patterns of missingness from baseline up to Month 6 will be provided as well as a figure presenting the mean change from baseline in mSLEDAI-2K for study completers and withdrawals by reason.

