7.2.6.6 Complete case analysis

Only data from subjects with the complete information available at all visits from baseline to Month 6 will be included in the analysis of the primary endpoint as described in Section 7.2.5 (based on the FAS).

7.2.6.7 *Hypothetical estimand analysis*

This supplementary analysis does not use the treatment policy strategy to account for treatment discontinuation that is used for the primary analysis estimand, but rather, the hypothetical strategy. This means that all assessments collected after premature treatment discontinuation are not included in the analysis.

The analysis will be conducted in the same way as the primary analysis as described in Section 7.2.5 (based on the FAS).

7.2.6.8 *Analyses based on SLEDAI-2K*

7.2.6.8.1 *Variable*

The derivation of the ‘full’ SLEDAI-2K is based on the derived mSLEDAI-2K scores of the primary endpoint [see Section 7.2.1], including baseline and Month 1 to Month 6 scores, and the leukocyte value (from the central laboratory) at the corresponding visit.

If leukopenia is present at the corresponding visit the SLEDAI-2K score derives as:

$$\text{SLEDAI-2K at Visit X} = \text{mSLEDAI-2K at Visit X} + 1.$$

If leukopenia is not present or the leukocyte data are missing at the corresponding visit the SLEDAI-2K score is derived as:

$$\text{SLEDAI-2K at Visit X} = \text{mSLEDAI-2K at Visit X}.$$

Leukopenia is defined as a leukocyte value of $< 3000 \times 10^9/\text{L}$ (per visit).

7.2.6.8.2 *Analysis*

The analysis of the primary endpoint as described in Section 7.2.5 will be conducted on the SLEDAI-2K.

7.2.6.9 *Dose-response analysis*

7.2.6.9.1 *Dose-response analysis*

The objective of this supplementary analysis is to assess overall dose-response using modeling and multiple comparison procedures on the primary efficacy endpoint (change in mSLEDAI-2K from baseline to Month 6).

7.2.6.9.2 *Hypothesis and model*

The null hypothesis is that there is no dose response for the primary efficacy endpoint from baseline to Month 6, and the alternative hypothesis is the existence of a dose response:

$$H_0: p_d \geq p_{\text{placebo}} \text{ for all doses } d = 0.5, 1, 2, 4 \text{ mg}$$

vs

$$H_1: p_d < p_{\text{placebo}} \text{ for at least 1 dose } d = 0.5, 1.0, 2.0, 4.0 \text{ mg}$$

To meet the objective of defining a dose response on the reduction of mSLEDAI-2K from baseline to Month 6, the null hypotheses must be rejected with an exploratory one-sided significance level of 5%.

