All statistically significant models (i.e., with a multiplicity adjusted p-value < 0.05) will be fitted in the Mod step and for each model AIC will be calculated. The smaller the value of AIC (= model deviance + 2 times the number of model parameters), the better the fit. The analysis will be performed using the R *DoseFinding* package [Bornkamp 2016].

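### The MCP-Mod confidence band treats the AIC-selected model as fixed in advance, so under every candidate shape its nominal 95% limits under-cover at one or more middle doses

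*SAP*

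**What the plan says.** SAP 7.2.6.9 applies MCP-Mod to the change in mSLEDAI-2K at Month 6. Table 5 lists it as a supplementary estimator. Section 7.2.6.9.2 sets the bar for a dose-response signal: "the null hypotheses must be rejected with an exploratory one-sided significance level of 5" percent. The five candidates are in Table 6 and in the code: "mods2 <- Mods(linear = NULL, linlog = NULL, emax = 1, sigEmax = c(1.5, 0.3), logistic" with parameters 1.5 and 0.3.

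Models that pass the contrast test "will be fitted in the Mod step and for each model AIC will be calculated". AIC is defined there as deviance plus twice the number of parameters. In 7.2.6.9.5 the `MCPMod` call uses AIC selection and `Delta=1.5`. The one selected model is refitted with `fitMod` to the same estimates and covariance matrix. The limits are then formed by "pred$LB <- pred$fit - qnorm(0.975)*pred$se.fit" and its upper counterpart. The text says the selected model will be fitted with the `fitMod` "function and plotted together with the LSM estimates and confidence intervals from the primary analysis".

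The target dose is among the summarised outputs. No interval for it is specified, and nothing in the section allows for the selection step.

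**The concern.** `se.fit` from the refitted model measures uncertainty in that model's parameters, given that its shape is correct. Here the shape was chosen from the same five means. If another shape is true, the selected curve is off-centre at some doses and its standard error does not show it.

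The AIC penalty makes this common. Linear and linear-in-log have two parameters, Emax three, sigmoidal Emax and logistic four. A four-parameter curve must lower the deviance by more than 2 × (4 − 2) = 4 to beat a straight line, which is a lot to ask of five noisy means.

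At stake is how firmly readers take the modelled response between placebo and 4 mg, and the target dose read from the same curve. The band appears beside arm-wise intervals that do not depend on selection, so two kinds of interval that look alike have different validity.

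**Working it through.** **Inputs from the SAP.** Section 2.1: "Approximately 325 adult subjects with SLE will be randomized in a 1:1:1:1:1 ratio", so 325 / 5 = 65 per arm. Section 7.2.3: "it is expected that 6% of subjects will have a missing mSLEDAI-2K result at Month 6", so 65 × 0.94 = 61.1, about 61 evaluable per arm. Doses are 0, 0.5, 1, 2 and 4 mg. Candidate shapes are those of Table 6, with linear-in-log as log(dose + 0.5).

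**Assumptions, not in the documents.** SD of change 4 or 5; effect at 4 mg of −1.5 (the SAP's Delta) or −2; independent means with SE = SD/√61 (0.512 at SD 4, 0.640 at SD 5); bounds for the non-linear parameters; each candidate in turn as the truth.

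**The nominal level.** `qnorm(0.975)` = 1.96, so the limits are nominally 95% pointwise. With the correct model fixed in advance (linear or Emax), simulated coverage of fit ± 1.96 × SE is 94.5-97%. The formula is sound when nothing is selected.

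**One cell by hand.** Take the logistic candidate as truth, −2 points at 4 mg, SD 4.
- As fractions of the 4 mg effect, the true values at 0, 0.5, 1, 2 and 4 mg are 0, 0.028, 0.153, 0.840 and 1, with mean 0.404.
- Doses have mean 1.5 and deviations −1.5, −1, −0.5, 0.5 and 2.5, with sum of squares 10.
- The fitted slope is (−0.028 − 0.077 + 0.420 + 2.5)/10 = 0.2816 per mg, so the linear fit at 2 mg is 0.404 + 0.5 × 0.2816 = 0.545.
- The error is (0.840 − 0.545) × 2 = 0.59 points.
- The linear model's SE at 2 mg is 0.512 × √(1/5 + 0.25/10) = 0.243, so the half-width is 1.96 × 0.243 = 0.48. The arm-wise interval has half-width 1.96 × 0.512 = 1.00.

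When a straight line is fitted to this truth, the band at 2 mg is under half as wide as the arm-wise interval, and its expected centre misses by more than its half-width.

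**How often the wrong shape is kept** (effect/SD 0.375 to 0.5, trials with a selected model):
- Logistic truth: logistic 19-24%, linear or linear-in-log 71-77%.
- Emax truth: Emax 16-18%, linear or linear-in-log 73-75%.
- Sigmoidal Emax truth: sigmoidal Emax 7-12%, linear or linear-in-log 41-48%.

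**The whole procedure.** Simulate five means, apply the one-sided 5% maximum-contrast test (critical value about 1.96), fit the significant models, take the lowest AIC, and form fit ± 1.96 × SE. Coverage depends on the effect only through effect/SD, so the table shows the two ends of the assumed range. Entries are the lowest coverage among 0.5, 1 and 2 mg.

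| True shape | −2 points, SD 4 (ratio 0.50) | −1.5 points, SD 5 (ratio 0.30) |
|---|---|---|
| Linear | 90% | 93% |
| Linear-in-log | 90% | 92% |
| Emax | 87% | 90% |
| Sigmoidal Emax (at 0.5 mg) | 79% | 82% |
| Logistic | 64% | 87% |

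Between these ends (ratio 0.375 to 0.40), the logistic truth at 2 mg gives about 75-80%. Coverage at 2 mg under linear-in-log, Emax and sigmoidal Emax truths, and at 0.5 mg under linear, linear-in-log and Emax truths, is 91-96%. Arm-wise intervals conditioned on the same contrast test keep 94-96%, so conditioning on the test is not the cause.

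**Target dose.** Under an Emax truth with ED50 = 1 and −2 at 4 mg, Emax × 4/5 = 2 gives Emax = 2.5. Then 2.5d/(1 + d) = 1.5 gives a true target dose of 1.5 mg. The selected-model estimate at SD 4 had a 10th to 90th percentile range of about 0.35 to 3.05 mg.

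**After the fix.** Repeating the AIC choice in each of 400 parametric draws gave 92-97% coverage at all doses and shapes, with bands 2-42% wider. A separate run (SD 3 to 5, an assumed offset of 0.04, AIC over all five models) gave 91-99% at 0.5, 1 and 2 mg; its worst cell rose from 58% to 95%.

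**The case against.** The strongest reply has three parts.

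First, the size is not a property of the documents. They give no SD, and the only effect-size figure is Delta = 1.5. A reader might infer from the lowest cells that the band misses the mid-dose response in a third of trials. The documents do not support that. Values below about 75% arise only for the steep logistic at 2 mg with the larger effect/SD ratio. For linear, linear-in-log and Emax truths the shortfall is a few points, and many cells are near nominal. The coverage also refers only to trials that pass the contrast test, which at ratio 0.30 is about half to two-thirds of them. All of this stands.

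Second, the analysis is supplementary with an exploratory significance level. The Hochberg and hierarchical tests in 7.1.1 and the arm-wise differences in 7.2.5 do not use the band, no dose-selection rule is tied to it, and the arm-wise intervals are on the same plot. This stands too, and it limits the consequence.

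Third, a band conditional on the selected model is a legitimate display if labelled so. That is true, but the SAP plans no such label, and the multiplier gives the limits an ordinary 95% meaning. Nor is the steep logistic an outside stress case: it is one of the plan's own five candidates. The mechanism therefore remains.

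**Conclusion.** The point holds for the supplementary MCP-Mod display. The limits ignore model selection, and the nominal 95% band under-covers at one or more middle doses under each of the plan's candidate shapes. The shortfall is small for linear and linear-in-log truths, moderate for Emax, clear for sigmoidal Emax at 0.5 mg, and large for the steep logistic when the effect is about half an SD.

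The figures rest on an assumed SD of 4 to 5, an assumed 1.5 to 2 points at 4 mg, 61 per arm, the Table 6 offset and conditioning on the contrast test. Simulation error is about a percentage point. It would be wrong to quote one coverage figure for the plan, or to infer that AIC nearly always takes a two-parameter curve: under a sigmoidal Emax truth it does so in roughly half of trials or fewer. It would also be wrong to read this as a threat to the primary or secondary conclusions. The change is worth making because this section is where the plan models the curve and estimates a target dose, and that dose has no planned interval.

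**What to change.** Keep the AIC-selected curve as the point estimate and replace the `pred$LB` and `pred$UB` lines:

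1. Draw at least 1000 vectors from N(`est`, `C`).
2. In each draw, refit the five candidates and repeat the AIC selection.
3. At each plotted dose, use the 2.5th and 97.5th percentiles of the selected-model predictions as the band.
4. Report the target dose for Delta = 1.5 with the percentile interval from the same draws, and state the share of draws with no target dose.

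Use the Table 6 offset (dose + 0.5) for linear-in-log in these draws and reconcile it with the `Mods` call, which passes no offset; the choice affects both selection and coverage. If the draws are not adopted, the least that should be done is to label the band as conditional on the selected model.

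The cost is a few lines of R on quantities that 7.2.6.9.4 already exports. The band becomes wider (about 2-42% in the simulation) and the target dose visibly uncertain. No confirmatory analysis changes.

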7.2.7 Subgroup analyses

The aim of these exploratory subgroup analyses, classifying subjects according to important baseline characteristics, is to explore the consistency of treatment effect in a variety of relevant subject subgroups to support the efficacy evaluation of cenerimod in this indication.

7.2.7.1 Variables

Subgroup variables are defined as in Section 5.5.

7.2.7.2 Analysis

The same model as for the main analysis described in Section 7.2.5 will be fitted per subgroup. Stratification factor OCS will not be included as a fixed effect in the model for subgroup analysis by daily dose of OCS.

Summary tables will be produced, similar to those produced for the primary efficacy analysis, by subgroup.

Forest plots will be produced, displaying the LSM differences for each dose vs placebo including 95% CIs at Month 6. The forest plot will include an ‘overall’ treatment effect, based on the primary efficacy analysis and a reference line for the zero effect.

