5.5 Subgroups

The category in **bold type** is the reference category used for the analysis of subgroups.

The following subgroup variables are defined according to protocol:

- **Stratification variable:** Daily dose of OCS (< **7.5 mg** or ≥ 7.5 mg prednisone equivalent) from IXRS system;
- **Stratification variable:** mSLEDAI-2K (< **10** or ≥ 10) from IXRS system;
- Sex (**male**/female);
- Geographical region (**Europe**, US, Rest of World);
- Age (< **65 years** vs ≥ 65 years) at Screening;
- Belimumab treatment status (**‘treated’** vs ‘not treated’) at Screening;
- Race (**White**, American Indian or Alaska Native, Asian, and Black).

Both stratification variables are taken from the IXRS system; sex, age (< 65 years vs ≥ 65 years) and race are taken from the Demographics eCRF page. Region is derived based on the country of the sites. Belimumab treatment status is derived as a binary variable based on coding from the Previous/Concomitant Medication eCRF page.

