7.2.5 Main analysis

The primary statistical analysis will be performed using the FAS, according to the intention-to-treat approach.

The null hypotheses for the primary endpoint will be tested using an MMRM on all available changes from baseline in mSLEDAI-2K for post-baseline scores from Months 1 through 6.

The following fixed effects will be included in the model:

- Treatment group.
- Month.
- Baseline mSLEDAI-2K score.
- Treatment group by month interaction.
- Baseline mSLEDAI-2K score by month interaction (as continuous variable).
- Stratification factor OCS (from IXRS).

The stratification factor mSLEDAI-2K at Screening will not be included in the model as the continuous baseline value is already included in the model.

A restricted maximum likelihood approach in combination with the Newton Raphson Algorithm will be used.

An unstructured (UN) covariance matrix will be used to account for the correlation between repeated measurements from the same subject. If this analysis fails to converge, the following structures will be tested in a subsequent order until model-convergence is achieved: heterogeneous Toeplitz (TOEPH); Toeplitz (TOEP); autoregressive (AR(1)); compound symmetry (CS). The Kenward-Roger approximation will be used to estimate denominator degrees of freedom.

The treatment effect for each cenerimod dose vs placebo will be estimated from the LSM differences for each dose vs placebo at Month 6 and their corresponding 95% CIs.

The hypothesis tests will be based on the associated p-values at the two-sided significance level of alpha of 5%, controlling for multiplicity using the Hochberg procedure as mentioned above.

This analysis will be implemented using the following SAS[®] code:

```
proc mixed method=reml;
  class subjid ocs treatment month;
  model change = ocs sledai_bl treatment month treatment*month sledai_bl*month / ddfm=kr;
  repeated month / type = UN subject=subjid(treatment);

  slice treatment*month / sliceby=month pdiff cl;
run;
```

Efficacy data of the primary endpoint will be summarized descriptively and listed using the FAS.

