12.5 Revision history

Version Date	Version	Implemented Change(s)
5-Aug-2019	1.0	New
27-Aug-2020	2.0	
 • Section 2.1: added paragraph on the echocardiography ancillary study. • Section 3.1.1: the final ICH E9 addendum was not available when version 1 of this SAP was prepared. The draft ICH E9 addendum did not include the “treatment condition of interest” attribute. This was now added in this SAP. • Section 4.1: clarified definition of ‘treatment received’ and updated analysis set labels to remove ‘TP1’ as these analysis sets are also used for analyses that combine data from TP1 and TP2. • Section 5.4.3: updated treatment groups for exploratory analyses of TP2 data and TP1 + TP2 data combined. Clarified treatment groups used in listings. • Section 6.1: updated to account for re-screening which was not allowed in previous protocol version. • Section 6.2.2: removed summary table of eligibility criteria. • Sections 6.3, 6.4, 6.5, 6.6, 6.9: data will be presented separately during TP1, during TP2 and during TP1 + TP2. • Section 6.6: added listing for subjects unblinded during the study; added summaries of DVs related to COVID-19 pandemic. • Section 6.7.2: clarified that analysis sets will be summarized separately by randomized group and treatment received. Separate tables for re-randomized groups added. Added tables for reasons of exclusion. • Section 6.8.1.2: added demographics by sex table. • Section 6.8.2.2: clarified that stratification factors will be presented as shift table. • Section 6.8.6: added summaries for concomitant at baseline therapies; clarified definition of SLE therapies; clarified date imputation; added summary of changes in background medications. • Section 7.2.3: added patterns of missingness table and figure showing mean change from baseline by study completers and withdrawals. • Section 7.2.5: added further details for MMRM specification. • Section 7.2.7.2, 7.3.1.7: clarified subgroup analyses (separate models per subgroup). • Sections 7.3.1.3, 7.3.2.3: added patterns of missingness table. • Section 7.3.1.5: added further details for GLMM specification. • Sections 7.3.1.6.2, 7.3.1.6.3, 7.3.2.6.2, 7.3.2.6.3: added additional sensitivity analyses. • Sections 7.5.2.2, 7.5.3.2, 7.5.4.2, 7.5.5.2, 7.5.6.2, 7.5.8.2, 7.5.9.2: clarified that only re-randomized groups are included in models of TP2 data.

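### Subgroup analyses aim at consistency of effect but report only within-level dose effects, so no difference between levels is estimated and the reference categories in SAP 5.5 are unused

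*SAP*

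**What the plan says.** SAP 7.2.7 calls the subgroup analyses exploratory and states that their aim "is to explore the consistency of treatment effect in a variety of relevant subject subgroups".

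SAP 7.2.7.2 gives the method: "The same model as for the main analysis described in Section 7.2.5 will be fitted per subgroup". The revision history (SAP 12.5, version 2.0) leaves no doubt that the fits are separate: "clarified subgroup analyses (separate models per subgroup". The outputs are summary tables by subgroup and a forest plot of each dose-minus-placebo difference at Month 6 with its 95% CI, together with the overall effect and a line at zero.

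SAP 7.3.1.7 does the same for SRI-4 with odds ratios, and 7.3.2.7 carries this over to BILAG-2004.

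SAP 5.5 lists seven subgroup factors, sets one level of each in bold, and says that the bold level "is the reference category used for the analysis of subgroups".

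**The concern.** Consistency is a question about the difference in effect between levels. The plan produces an estimate and interval within each level and none for that difference. A reference category matters only where levels are compared, and no planned subgroup model contains a subgroup term. The 5.5 sentence therefore has nothing to act on.

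Without a contrast, readers will tend to judge consistency by which intervals cross the no-effect line. That depends heavily on how many subjects are in the level. A factor can look inconsistent when the effect is the same throughout, and wide overlapping intervals can be taken as evidence of consistency when they carry little information.

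**Working it through.** The SAP states no figure for the subgroups, so there is none to reproduce. Splits between levels and overall power are not given; they are assumptions, shown as ranges.

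**1. What the plan produces.** Levels in 5.5: OCS 2, mSLEDAI-2K 2, sex 2, region 3, age 2, belimumab 2, race 4, which is 17. With four doses that is 17 × 4 = 68 within-level intervals for the primary endpoint. Between-level contrasts planned: none. Against the bold references there would be 17 − 7 = 10 non-reference levels, so 10 × 4 = 40 contrasts.

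**2. How often the display disagrees when the effect is identical.** Take a two-level factor with share *f* of subjects in one level, equal variance, and the same true effect in both. Let λ = 1.960 + 0.842 = 2.802, which is 80% power for one dose at two-sided 5%. The level with share *f* has a CI excluding zero with probability *p* = Φ(λ√f − 1.960). For the other level, *q* = Φ(λ√(1 − f) − 1.960). The probability that exactly one excludes zero is p(1 − q) + q(1 − p).

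| Split | p | q | One excludes zero, the other does not (80% power) | Same, at 90% power |
|---|---|---|---|---|
| 50/50 | 0.51 | 0.51 | 0.50 | 0.47 |
| 20/80 | 0.24 | 0.71 | 0.61 | 0.63 |
| 10/90 | 0.14 | 0.76 | 0.68 | 0.74 |

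**3. Precision of the missing contrast.** Relative to the overall dose-placebo SE, the SE within a level is 1/√f. Levels are disjoint, so the SE of the difference is √(1/f + 1/(1 − f)) = 1/√(f(1 − f)).

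| Split | SE of contrast / overall SE | Power if the interaction is as large as the overall effect (overall power 80% / 90%) |
|---|---|---|
| 50/50 | 2.0 | 29% / 37% |
| 20/80 | 2.5 | 20% / 25% |
| 10/90 | 3.3 | 13% / 16% |

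The contrast is useful as an estimate with its uncertainty, not as a test.

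**4. Small levels.** The model in SAP 7.2.5 has 1 + 1 + 1 + 4 + 5 + 20 + 5 = 37 fixed-effect parameters (intercept, OCS, baseline, treatment, month, treatment by month, baseline by month) and 6 × 7 / 2 = 21 unstructured covariance parameters. Leaving aside the shared OCS term, each visit uses 6 mean parameters (five arms and a baseline slope). With complete data the 6 × 6 residual matrix has full rank only if n − 6 ≥ 6, so n ≥ 12; a numerical check gave rank 5 at n = 11 and rank 6 at n = 12. SAP 2.1 says: "Approximately 325 adult subjects with SLE will be randomized in a 1:1:1:1:1 ratio". Twelve subjects are 12/325 = 3.7%. The OCS term and missing visits raise the threshold slightly; SAP 7.2.3 says "it is expected that 6% of subjects will have a missing mSLEDAI-2K result at Month 6".

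An empty arm is a separate problem. Under simple random 1:1:1:1:1 allocation, the probability of at least one empty arm among *n* subjects is 5(0.8)ⁿ − 10(0.6)ⁿ + 10(0.4)ⁿ − 5(0.2)ⁿ: 0.48 at n = 10, 0.26 at n = 13, 0.14 at n = 16 and 0.004 at n = 32.

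**The case against.** The best defence is that these are exploratory analyses, that separate models were a deliberate clarification, and that the forest plot shows the overall effect, so each level can be read against it and not only against zero. Because levels are disjoint, a reader could also subtract two within-level estimates and combine their SEs. The bold-reference sentence may be no more than an unused remnant. SAP 5.5 refers to the protocol for the subgroup variables, and the protocol document supplied is the COVID-19 addendum, so a between-level analysis in the main protocol cannot be excluded.

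Much of this stands, and it limits the importance of the point. It does not remove it: the SAP does not plan the subtraction, and reading a level against the overall effect gives no interval for the difference between levels.

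Replacing the separate fits by a pooled model would also be a trade-off. Pooling assumes one within-subject covariance and one baseline slope for all levels, which separate fits avoid. It cannot supply a missing arm either.

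A reader might also infer that the smallest levels, such as age 65 and over or the smaller race groups, cannot support the model. The documents do not support that. They give no level counts, and SAP 7.2.5 has a covariance fallback (TOEPH, TOEP, AR(1), CS) if the unstructured fit does not converge.

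**Conclusion.** The point holds as a gap between aim and output. Consistency is the stated aim, no difference in effect between levels is estimated for the primary endpoint, SRI-4 or BILAG-2004, and the 5.5 reference categories are unused. With an identical true effect, the planned intervals would disagree about excluding zero with probability about 0.5 to 0.7. This assumes 80% or 90% overall power for a dose, equal variance, and splits from 50/50 to 10/90.

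For small levels only a conditional statement is justified. A level with fewer than about 12 subjects may not support the unstructured model, and a dose contrast is not estimable if that dose arm or the placebo arm is empty in the level. Whether either occurs depends on counts that the documents do not give.

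The consequence is limited to the interpretation of exploratory results. The primary tests and their Type I error control are untouched.

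**What to change.** Keep the within-level forest plots. For each factor and dose, add the Month 6 difference in treatment effect between each level and the bold 5.5 reference level, with a 95% CI. For SRI-4 and BILAG-2004 this is a ratio of odds ratios. Label it exploratory and not a test.

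Take it from one FAS model per factor, restricted to subjects in the listed levels. The restriction matters for race: 5.5 lists four levels, while SAP 6.8.1.1 collects further categories. The model is that of 7.2.5 plus subgroup, subgroup-by-month, treatment-by-subgroup and treatment-by-month-by-subgroup terms. Where the factor is itself a stratification variable in the model, it enters once. Use the analogous GLMM for the binary endpoints.

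If only separate fits are kept, take the difference of the two independent estimates with SE = √(SE₁² + SE₂²), on the log odds ratio scale for the binary endpoints. State that a dose contrast is reported as not estimable where an arm it needs is empty.

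The cost is SAP wording, one program and 40 further intervals for the primary endpoint. The pooled model carries the common covariance and baseline-slope assumption, and the intervals will be wide.
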